# Number of Fertilised Oocytes and Fertilisation Rate

An oocyte is defined as correctly fertilised if it is scored as 2 pronuclei (PN) on day 1 after oocyte retrieval. The mean number of correctly fertilised oocytes will be compared between treatments using the same analysis method as for the primary endpoint.

For subjects with >0 oocytes retrieved, the rate of correctly fertilised oocytes to oocytes retrieved will be estimated and compared between treatments using a negative binomial regression model with treatment and AMH level at stimulation day 1 (AMH <15 pmol/L, AMH  $\ge$ 15 pmol/L, or missing) as factors and the number of retrieved oocytes (log-transformed) as an offset. The treatment difference in fertilisation rate and the associated 95% confidence interval will be derived using the delta method.

# Number of Blastocysts (Total and by Quality)

The total number and quality of blastocysts on day 5 or day 6 will be compared between treatments using the same negative binomial regression model as used for the primary endpoint.

# **Total Gonadotropin Dose and Number of Stimulation Days**

Tables will be produced overall and by AMH level at stimulation day 1 (AMH <15 pmol/L, AMH  $\geq$ 15 pmol/L, or missing) for the total gonadotropin dose, the average daily dose, the number of stimulation days and the occurrence of dose adjustments during stimulation (i.e. number of dose increases and decreases).

The number of stimulation days will be compared between treatments using an analysis of variance model with treatment and AMH level at stimulation day 1 (AMH <15 pmol/L, AMH  $\ge$ 15 pmol/L, or missing) as factors.

# Early OHSS (Overall and by Grade) and/or Preventive Interventions for Early OHSS

Early OHSS is defined as OHSS with onset  $\leq 9$  days after triggering of final follicular maturation (including OHSS with onset during stimulation or before triggering). Incidence of early OHSS will be summarised by classification (mild, moderate, severe) and grade (1, 2, 3, 4, 5).

Preventive interventions for early OHSS (i.e. cycle cancellation due to excessive ovarian response, triggering of final follicular maturation with GnRH agonist based on follicular development and/or serum estradiol criteria, and/or administration of dopamine agonist if  $\geq 20$  follicles of  $\geq 12$  mm is observed) will be summarised.

The tabulations will be produced overall and by AMH level at stimulation day 1 (AMH <15 pmol/L, AMH  $\ge$ 15 pmol/L, or missing) and will include both treatment groups and a total column.

#### **10.3** Exploratory Assessment

#### **Blood Collection for Potential Biomarkers**

Potential future analysis of possible biomarkers associated with ovarian response will be reported separately from the clinical trial report.

#### **10.4** Follow-up Assessments

Follow-up assessments will be based on the FAS. Unless otherwise specified, summary tables will include both treatment groups and a total column. An overview of the methods used for follow-up assessments is provided in Table 10-2 and described in detail below.

Table 10-2	Overview of analysis methods for follow-up assessments
-------------------	--

	Analysis method		
Follow-up Assessments	Summary tables	Logistic regression	Negative binomial regression
Clinical pregnancy by type	Х		
Vital pregnancy	Х		
Pregnancy rate	Х	X	
Implantation rate	Х		Х
Incidence of late OHSS	Х		

#### Pregnancy

For subjects with a clinical pregnancy (at least one gestational sac 5-6 weeks after transfer), the type of clinical pregnancy (intrauterine or ectopic) will be described. For subjects with a vital pregnancy (at least one intrauterine gestational sac with fetal heart beat 5-6 weeks after transfer), the number of intrauterine gestational sacs with fetal heart beat will also be described.

Pregnancy rates in the first transfer cycle will be compared between treatments using a logistic regression model with treatment and age group (<35, 35-37, or 38-40 years) as factors. The estimated probabilities, difference in probabilities and 95% CIs for the estimated difference in probabilities will be presented based on the delta method. In these analyses subjects with no transfer or missing data on pregnancy will be regarded as non-pregnant.

#### Implantation rate

The implantation rate (i.e. number of gestational sacs 5-6 weeks after transfer relative to number of blastocysts transferred) in the first transfer cycle will be estimated and compared between treatments using a negative binomial regression model with treatment and age group (<35, 35-37, or 38-40 years) as factors and the number of transferred blastocysts (log-transformed) as an offset. The treatment difference in implantation rate and the associated 95% confidence interval will be derived using the delta method. This analysis is based on subjects with transfer only and is therefore not randomisation based. The treatment difference for implantation rates is expected to be consistent with the treatment difference for pregnancy rates. If this is not the case, the reason for differences will be further explored by including e.g. day of transfer as a factor in the analysis model.

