#### Follow-up Assessments

• Clinical pregnancy rate (at least one gestational sac 5-6 weeks after transfer) in the first transfer cycle

• Implantation rate (number of gestational sacs 5-6 weeks after transfer divided by number of blastocysts transferred) in the first transfer cycle

*Note:* the first transfer cycle covers cycles with transfer occurring within 3 months after start of stimulation

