#### Follow-up Period – First Transfer Cycle

Follow-up information will be collected from the subject's first transfer cycle, irrespective of whether the first transfer takes place in a fresh or frozen cycle. This follow-up covers cycles with the transfer procedure occurring within 3 months after start of stimulation.

[figure not shown]
Depending on blastocyst availability, it is expected that subjects who underwent triggering of final follicular maturation with hCG will undergo transfer on day 5 after oocyte retrieval and that

subjects who underwent triggering of final follicular maturation with GnRH agonist will undergo transfer in a frozen cycle using blastocysts cryopreserved on day 5 or day 6 after oocyte retrieval. The number of transferred blastocyst(s) in the first fresh or frozen cycle will be based on the subject's wishes and the investigator's recommendation and in accordance with local guidelines and/or regulations. The number and quality of transferred blastocyst(s) will be recorded. Luteal phase support in fresh and frozen cycles as well as potential other medicinal products for programming of frozen cycles will be in accordance with the site's clinical practice.

Clinical pregnancy in the first transfer cycle will be assessed by transvaginal ultrasound 5-6 weeks (35-48 days) after transfer, and the number of gestational sacs will be recorded. For subjects who undergo transfer in the fresh cycle, assessment of late OHSS (onset >9 days after triggering) will take place during the follow-up period.

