#### 10 EFFICACY

Unless otherwise specified, analyses of efficacy endpoints will be based on the FAS and summary tables for the primary and secondary efficacy endpoints will be presented in total and by treatment group. Continuous variables will be presented with number of subjects, mean, standard deviation, median, inter-quartile range, minimum, and maximum. Categorical variables will be presented with number and percentage of subjects within each specific category.

Results of statistical analyses will be based on least-squares means using the observed margins and include the estimated treatment difference (or ratio), a 95% confidence interval for the difference (or ratio), and the p-value for the test of no treatment difference. All analyses are of descriptive nature and no adjustments for multiple tests will be applied.

Missing observations for the endpoints number of oocytes retrieved, number of fertilised oocytes, and number of blastocysts will be replaced with zero (i.e. worst-case imputation technique) irrespective of the reason why data is not recorded. For pregnancy data, lack of data will be interpreted as a negative pregnancy.

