## **13 DEVIATIONS FROM THE PROTOCOL**

This SAP introduces the following changes to the analyses described in the trial protocol:

- A supplementary analysis of the primary efficacy endpoint using the PP analysis set (Section 10.1).
- Fertilisation rates (Section 10.2) and implantation rates (Section 10.4) will be estimated using negative binomial models with an offset to account for the differences in retrieved

oocytes and transferred blastocysts, respectively. This method was considered more appropriate than the mixed effects models described in the protocol as the proportion of subjects with a single observation is expected to be substantial.

• Exposure and treatment compliance (Section 9) will be tabulated for the Safety Analysis Set instead of the Full Analysis Set

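### SAP 10.4 fits implantation rate as a negative binomial count with no robust variance: at assumed rates of 20-50% its 95% CI is about 12-41% too wide if nearly all transfers are single, and about 3-31% with 40% double transfers (correlation 0.3)

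*Combined protocol and SAP*

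**What the plan says.** SAP 2.2 defines the endpoint: "Implantation rate (number of gestational sacs 5-6 weeks after transfer divided by number of blastocysts transferred) in the first transfer cycle". SAP 10.4 (Implantation rate) models the sac count by negative binomial regression, with treatment and age group "as factors and the number of transferred blastocysts (log-transformed) as an offset". Only subjects with a transfer are included, and the difference in rates and its 95% CI come from the delta method. SAP 10 adds, for statistical analyses generally, a 95% CI "and the p-value for the test of no treatment difference". None of SAP 10, 10.4 or 13 names a robust, sandwich or binomial variance.

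Protocol 9.11 had planned a mixed-effects logistic model, which has binomial variance. SAP 13 replaces it because "the proportion of subjects with a single observation is expected to be substantial".

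In the same SAP section, clinical pregnancy keeps a binomial analysis: "Pregnancy rates in the first transfer cycle will be compared between treatments using a logistic regression model with treatment and age group". The two results are then to be set against each other: "The treatment difference for implantation rates is expected to be consistent with the treatment difference for pregnancy rates". If they disagree, the reasons are to be explored.

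The transfer mix is not fixed. SAP 3.1 states: "The number of transferred blastocyst(s) in the first fresh or frozen cycle will be based on" the woman's wishes, the investigator's advice and local rules.

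**The concern.** A negative binomial model has variance mu + k·mu², with k at or above zero in the usual parameterisation, so its variance is never smaller than the mean. One transferred blastocyst yields essentially no sac or one sac, with variance p(1-p), which is smaller than the mean p. No admissible k can represent that. The estimate of k goes to zero, the model becomes Poisson, and the model-based standard error is too large.

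A large share of single observations is a fair reason to drop a subject-level random effect. It is also the situation in which a count variance fits worst.

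Two things are at stake. The interval labelled 95% would cover more than 95%, and the p-value would be too large. And for a single transfer, implantation and clinical pregnancy are nearly the same event, yet the SAP applies a Poisson-like variance to one and a binomial variance to the other, so the two intervals would differ in width partly because of the variance rule.

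**Working it through.** **Plan's own figure.** The documents state no precision for implantation rate. The only precision figure is for the primary endpoint (SAP 3.2), and it reproduces: 1.96 × 6.0 × sqrt(1/200 + 1/100) = 1.44 oocytes.

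**Inputs.** Model, offset, factors, delta method and transfer-only population: SAP 10.4. Assumed, because the documents give no values: implantation rate p = 0.20 to 0.50; share f of women with two blastocysts transferred, 0 to 40%; within-woman correlation r = 0.3 or 0.5; 160 vs 80 women with a transfer.

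**Closed form.** Consider one arm with n women, n(1+f) blastocysts and k = 0.

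- Model variance of the rate: p / [n(1+f)].
- True variance: p(1-p)·[(1-f) + 2f(1+r)] / [n(1+f)²] = p(1-p)(1+f+2fr) / [n(1+f)²].
- SE ratio (model / true) = sqrt{ (1+f) / [(1-p)(1+f+2fr)] }. With f = 0 this is 1/sqrt(1-p).

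The ratio is the same in both arms if p, f and r are, so it carries over to the difference.

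| Transfer mix | p=0.20 | p=0.30 | p=0.40 | p=0.50 |
|---|---|---|---|---|
| All single | 1.118 | 1.195 | 1.291 | 1.414 |
| 5% double, r=0.3 | 1.102 | 1.179 | 1.273 | 1.394 |
| 15% double, r=0.3 | 1.077 | 1.151 | 1.243 | 1.362 |
| 40% double, r=0.3 | 1.033 | 1.104 | 1.193 | 1.307 |
| 40% double, r=0.5 | 0.986 | 1.054 | 1.139 | 1.247 |

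Where the ratio is below 1, the fitted k rises above zero and the excess is about nil.

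**In percentage points, 160 vs 80.** Example, all single, p = 0.30: planned 1.96 × sqrt(0.30 × (1/160 + 1/80)) = 14.7; correct 1.96 × sqrt(0.21 × (1/160 + 1/80)) = 12.3.

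| 95% CI half-width, planned vs correct | p=0.20 | p=0.30 | p=0.40 | p=0.50 |
|---|---|---|---|---|
| All single | 12.0 vs 10.7 | 14.7 vs 12.3 | 17.0 vs 13.1 | 19.0 vs 13.4 |
| 40% double, r=0.3 | 10.1 vs 9.8 | 12.4 vs 11.3 | 14.3 vs 12.0 | 16.0 vs 12.3 |

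With no true difference, a nominal 5% test would reject in about 2.8, 1.9, 1.1 and 0.6% of trials (all single), or 4.3, 3.1, 1.9 and 1.0% (40% double, r = 0.3).

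**Simulation of the planned model.** Negative binomial maximum likelihood, age factor (assumed shares 50/25/25%, relative rates 1.15/1.00/0.70), observed margins, delta method, 160 vs 80, 4,000 fits per cell:

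| Mix | Model SE / empirical SD at p=0.2, 0.3, 0.4, 0.5 | Coverage of the planned 95% CI |
|---|---|---|
| All single | 1.11, 1.22, 1.32, 1.46 | 96.7, 98.2, 99.0, 99.6% |
| 40% double, r=0.3 | 1.04, 1.09, 1.21, 1.34 | 95.5, 97.1, 98.4, 99.1% |
| 40% double, r=0.5 | 1.02, 1.06, 1.16, 1.26 | 95.5, 96.0, 97.6, 98.5% |

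The dispersion estimate was zero in every all-single fit and in 92-100% of fits with 40% double and r = 0.3. With r = 0.5 it was zero in 50% at p = 0.20 and in 99-100% above that. A sandwich variance on the same fits gave SE ratios of 0.97-1.01 and coverage of 94.2-95.1%. A separate, smaller simulation (500 trials per scenario) gave coverage of 95-99% for the model-based CI and 93-96% for the robust one.

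**More sacs than blastocysts.** With 2% of implantations splitting, 15% double and r = 0.3, the planned ratios at p = 0.3, 0.4 and 0.5 were 1.15, 1.20 and 1.37. Robust coverage was 93.7-95.2% without capping the sac count.

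**Fertilisation rate.** SAP 10.2 uses the same device, "as factors and the number of retrieved oocytes (log-transformed) as an offset", and SAP 13 gives the same reason for it. The reason does not fit. A negative binomial with mean 11.8 and SD 5.7 or 6.0 (SAP 3.2) puts 0.47% or 0.63% of women at exactly one oocyte; those planning values come from women aged 22-37, while this trial enrols to 40. No excess width is claimed there: at an assumed fertilisation rate of 0.6 and 11.8 oocytes, the binomial variance reaches the Poisson variance once 0.4 × (1 + 10.8r) = 1, that is at r of about 0.14.

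**The case against.** The algebra is hard to dispute; the case against concerns weight and conditionality.

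- **Low stakes.** The SAP calls all its analyses descriptive, implantation rate is neither primary nor secondary, and the analysis is acknowledged not to be randomisation based. This stands, and it limits the importance of the point.
- **The consistency check concerns differences, not widths.** The point estimates are not biased, so comparing them is not distorted. The intervals would differ anyway, because the pregnancy analysis counts women without a transfer as non-pregnant. This also stands. What remains is that a reader judging agreement from the two intervals sees a gap in width that comes partly from the variance rule.
- **The sizes are assumed.** SAP 13 says substantial, not nearly all, and nothing caps double transfers at 40%. With 60% double and r = 0.5 the ratios are about 0.95, 1.02, 1.10 and 1.21. So the excess runs from nil to about 40%. The strict 12-41% is for all single transfers; 5% double gives 10-39%, a change of about two points.
- **Silence is not a wrong choice.** The delta method works with either covariance matrix, and software that allowed negative dispersion would behave differently. True, but a plan that names only the model is ordinarily run with the model-based variance and k ≥ 0. If a robust variance is intended, the SAP should say so.

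**Conclusion.** The concern holds. As written, SAP 10.4 gives implantation rate a model-based count variance that is too large when most transfers are single. At implantation rates of 20-50% the 95% CI is about 12-41% too wide if all or nearly all transfers are single, and about 3-31% too wide with 40% double transfers and correlation 0.3. With 40% double and correlation 0.5 the range is about 0-25%. True coverage is roughly 97-99.6% with all single transfers, against the stated 95%.

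These sizes rest on assumed rates, transfer mix and correlation, and on dispersion bounded at zero. The error is conservative, does not bias the estimate, and no trial conclusion depends on it. It should still be corrected, because the stated confidence level is wrong over most of the range examined and the correction is trivial. For fertilisation rate only the stated reason is at fault; no defect of known size is shown.

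**What to change.** Keep the log-link model, offset, age group, observed margins and delta method. Add one sentence to SAP 10.4: the CI and p-value for implantation rate use a subject-level robust (sandwich) variance, and if the dispersion estimate is zero, the Poisson fit with the same robust variance is reported. The endpoint definition in SAP 2.2 does not change, and no cap on sacs is needed.

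In SAP 13, limit the single-observation reason to implantation rate. The same robust-variance sentence may be added for fertilisation rate, for consistency only.

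Cost: one added sentence, a small edit to SAP 13 and one option in the model statement. No new data are needed.

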# Late OHSS

For subjects who undergo transfer in the fresh cycle, incidence of late OHSS will be summarised by classification (mild, moderate, severe) and grade (1, 2, 3, 4, 5). Late OHSS is defined as OHSS with onset >9 days after triggering of final follicular maturation. The tabulations will be produced overall and by AMH level at stimulation day 1 (AMH <15 pmol/L, AMH  $\geq$ 15 pmol/L, or missing) and will include both treatment groups and a total column.

## **OHSS (Early and/or Late)**

OHSS for each treatment group will be tabulated by classification (mild, moderate, severe) and grade (1, 2, 3, 4, 5). The following endpoints are defined:

- Subjects with early and/or late OHSS
- Subjects with early and/or late OHSS of moderate or severe grade

For each endpoint the proportion of subjects will be tabulated by treatment.

# 11 SAFETY

## 11.1 General Considerations

Safety parameters will be evaluated for the safety analysis set, i.e. data will be reported according to actual treatment received. Tabulations will be prepared overall, i.e. not by AMH level at stimulation day 1.

## 11.2 Adverse Events

Adverse events will be grouped according to start of IMP as follows:

• Pre-treatment adverse event, i.e. any adverse event occurring after signed informed consent and before the first dose of IMP, or a pre-existing medical condition that worsens in intensity after signed informed consent but before the first dose of IMP.

• Treatment-emergent adverse event, i.e. any adverse event occurring after the first dose of IMP and before the end-of-trial visit, or a pre-treatment adverse event or pre-existing medical condition that worsens in intensity after the first dose of IMP and before the end-of-trial visit.

Treatment-emergent adverse events will be presented in summary tables and listings. Pre-treatment adverse events will be presented in a listing only. Treatment-emergent adverse events will be summarised overall and tabulated by System Organ Class (SOC) and Preferred Term (PT). The total number of subjects reporting an adverse event, the percentage of subjects with an adverse event, and the number of events reported will be described.

Summary tables will be produced for the following treatment-emergent adverse events: all adverse events, adverse events by causality (reasonable possibility / no reasonable possibility), adverse events leading to death, adverse events by intensity (mild / moderate / severe), adverse reactions by intensity (mild / moderate / severe), serious adverse events, adverse events leading to discontinuation, adverse events with an incidence of  $\geq 5\%$  in any treatment group, and non-serious adverse events with an incidence of  $\geq 5\%$  in any treatment group.

For adverse events, a worst-case approach will be used for causality, intensity, seriousness, and outcome, in case these would be missing. If the timing of the onset of an adverse event cannot be established in relation to IMP, it will be considered as a treatment-emergent adverse event.

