# 6.5 End-of-trial

For subjects who undergo triggering of final follicular maturation, the end-of-trial visit must take place 9-14 days after triggering to cover the assessments of early OHSS (onset  $\leq$ 9 days after triggering).

For subjects who do not undergo triggering of final follicular maturation, the end-of-trial assessments must be performed at the subject's last scheduled trial visit (or alternatively at a separate end-of-trial visit within 7 days of the last scheduled trial visit).

The following end-of-trial procedures / assessments must take place, irrespective of whether the subject discontinues the trial prematurely or completes it:

- Physical examination
- Gynaecological examination
- Recording of use of any concomitant medication
- Recording of adverse events

The assessments serve to document the subject's health at the end of the trial.

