# 7.4.5 Physical Examination

A complete physical examination will be performed at screening and end-of-trial. Information will be recorded for general appearance, central and peripheral nervous system, head and neck (including ears, eyes, nose, mouth, and throat), respiratory system, cardiovascular system, gastrointestinal system, lymphatic system, urinary system, musculoskeletal system, and skin.

At screening, each category will be evaluated as normal, abnormal not clinically significant or abnormal clinically significant. Abnormal clinically significant findings at screening must be reported in the Medical History Log.

At end-of-trial, potential changes from screening to end-of-trial will be evaluated for each category. In case of changes, these will be evaluated as normal, abnormal not clinically significant or abnormal clinically significant. Abnormal clinically significant changes from screening to end-of-trial must be recorded as adverse events.

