#### 8.2 Collection and Recording of Adverse Events

#### 8.2.1 Collection of Adverse Events

The investigator must monitor the condition of the subject throughout the trial from the time of obtaining informed consent until the last visit (end-of-trial visit). In addition, for subjects who undergo transfer in the fresh cycle, assessment of late OHSS (onset >9 days after triggering) will take place during the follow-up period.

The sources of adverse events cover:

- The subject's response to questions about his/her health (a standard non-leading question such as "How have you been feeling since your last visit?" is asked at each visit).
- Symptoms spontaneously reported by the subject.
- Investigations and examinations where the findings are assessed by the investigator to be clinically significant changes or abnormalities.
- Other information relating to the subject's health becoming known to the investigator (e.g. hospitalisation).

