# 8.2.2 Recording of Adverse Events

The investigator must record all adverse events in the Adverse Event Log provided for each subject in the EDC with information about:

- Adverse event description
- Date and time of onset (time can be omitted, if applicable) [note: if date of onset of an event is the same as the date of informed consent or date of IMP administration, time is important and should not be omitted]
- Intensity
- Causal relationship to IMP
- Action taken to IMP
- Other action taken
- End date and time (time can be omitted, if applicable)
- Outcome
- Seriousness

Each of the items in the Adverse Event Log is described in detail in the following sections.

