# Date and Time of Onset

The date of onset is the date when the first sign(s) or symptom(s) were first noted. If the adverse event is an abnormal clinically significant laboratory test or outcome of an examination, the onset date is the date the sample was taken or the examination was performed.

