# 8 PRIOR AND CONCOMITANT MEDICATION

Medications will be coded using the World Health Organization Drug Reference List and categorised as either

- Prior medication: medication taken exclusively prior to treatment (i.e. with stop date/time before date/time of first IMP administration)
- Concomitant medication: medication taken during the treatment period (i.e. medication that was not stopped before date/time of first IMP administration and not started after the end-of-trial visit)

If the timing of the dose of a concomitant medication cannot be established in relation to the administration of IMP, it will be considered as concomitant medication.

Prior and concomitant medication will be summarised by Anatomical Therapeutic Chemical Classification System (ATC) classification first level (alphabetically) and ATC classification second level for the FAS and produced by treatment group and in total.

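### Treatment-emergent adverse events stop before the end-of-trial visit, so examination findings recorded as adverse events at that visit enter no adverse event table or listing

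*Combined protocol and SAP*

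**What the plan says.** SAP 11.2 sorts adverse events into two groups. Pre-treatment events fall between consent and the first dose of IMP. Treatment-emergent events are "any adverse event occurring after the first dose of IMP and before the end-of-trial visit", or earlier conditions that worsen within the same limits. Pre-treatment events are only listed. Treatment-emergent events are tabulated and listed, and the SAP confines all the adverse event summary tables, including the one for serious events, to this group. Protocol 9.9 defines the two groups in the same words.

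The protocol also sets rules for the end-of-trial visit:

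- Collection of adverse events runs from consent until that visit (protocol 8.2.1).
- Both examinations and the recording of adverse events are mandatory there (protocol 6.5).
- For the physical examination, "Abnormal clinically significant changes from screening to end-of-trial must be recorded as adverse events" (protocol 7.4.5). Protocol 7.4.6 says the same for the gynaecological examination.
- Where the event is an abnormal laboratory test or an examination outcome, "the onset date is the date the sample was taken or the examination was performed" (protocol 8.2.2, Date and Time of Onset).

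**The concern.** The upper bound excludes the visit itself, yet the protocol creates adverse events at that visit and dates them to it. Those events belong to neither group, so no adverse event output is planned for them. Comparing the safety profiles of the two products is a secondary objective, and the events at stake come from the last scheduled safety examination.

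The abnormal examinations would still be listed under SAP 11.3, but that section does not present them as adverse events with intensity, causality or seriousness. Protocol 9.10 planned shift tables for both examinations; SAP 11.3 plans listings instead. OHSS apart, no SAP table would therefore count these findings by treatment group. A programmer would have to apply the literal rule and drop required events, or include them without documented authority.

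**Working it through.** This is a question of definitions, and the plan gives no figure to reproduce. The check applies the rules of SAP 11.2 to events with different onset dates.

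**Classification by onset**

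| Onset | Group under SAP 11.2 as written | Group if the visit is included |
|---|---|---|
| Day before the end-of-trial visit | Treatment-emergent | Treatment-emergent |
| Day of the visit, as an examination outcome | None | Treatment-emergent |
| Day after the visit | None | None |

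For triggered subjects the visit falls 9 to 14 days after triggering (protocol 6.5). The result is the same at day 9 and at day 14.

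**Does another rule bring these events back?**

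- *Default rule in SAP 11.2.* It begins "If the timing of the onset of an adverse event cannot be established in relation to IMP" and assigns such events to the treatment-emergent group. A finding at the end-of-trial visit is plainly after the first dose, so the rule does not apply.
- *Onset rule in protocol 8.2.2.* An event whose signs or symptoms were first noted on an earlier day takes that earlier date and stays treatment-emergent. The gap concerns events whose onset is the examination itself. Any other event dated to the visit day is affected only if no earlier clock time is recorded; protocol 8.2.2 allows the time to be left out in most cases.
- *OHSS tables in SAP 10.2 and 10.4.* OHSS with onset on the visit date is still counted there.

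**Subjects who were not triggered.** Their end-of-trial assessments are done at the last scheduled visit, "or alternatively at a separate end-of-trial visit within 7 days of the last scheduled trial visit" (protocol 6.5). If they are done at the last scheduled visit, it is unclear whether that visit is the cut-off. If it is, events first found by examination that day are also left out.

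**Comparison within the SAP.** SAP section 8 counts a medication as concomitant if it was not stopped before the first dose and "not started after the end-of-trial visit". That window includes the visit. A drug started on the visit day to treat a finding made that day would be tabulated, while the finding itself would not be. This suggests that *before* in SAP 11.2 is a drafting slip.

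**Size**

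- Categories re-evaluated at end-of-trial: 10 physical (protocol 7.4.5) + 7 gynaecological (protocol 7.4.6) = 17 per subject. This is what is exposed to the gap, not an estimate of events lost.
- One subject left out for a preferred term, at the planned arm sizes: 1/200 = 0.5 percentage points for REKOVELLE; 1/100 = 1.0 percentage point for GONAL-F.
- Assumed illustration: a term reported by 5 of 100 GONAL-F subjects, one of them only at the end-of-trial examination, goes from 5/100 = 5.0% to 4/100 = 4.0%. It then drops out of the tables of events with at least 5% incidence, unless the REKOVELLE arm reaches 5%.

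**The case against.** The best counter-argument is that SAP 11.2 introduces the grouping as one by start of IMP. On that view the two groups are meant to hold every event collected, and the end-of-trial visit merely marks the end of collection, so *before* can be read inclusively. The intent may well have been that. But the bound is explicit and stands in both the onset and the worsening clause, and nothing in the text says that the visit is included. The lead-in does not override it.

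The second argument is that the gap is narrow. The event must be clinically significant, new or worse since screening, without an earlier sign or symptom, not OHSS, and first found at this visit. An ongoing treatment-emergent event that is worse at the visit is not lost, because protocol 8.2.2 keeps it as one event at its highest intensity. Serious events are reported to pharmacovigilance within 24 hours whatever the SAP says (protocol 8.5.2). All of this stands. It limits the likely number of events and the safety risk, but it does not put the events into the planned tables.

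Third, including the visit still leaves events with onset after it in no group, among them some late OHSS. That is true, but late OHSS has its own tabulation in SAP 10.4, and general adverse event collection ends at the visit. The change makes the analysis window match the collection window.

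**Conclusion.** The concern holds. Followed literally, SAP 11.2 leaves adverse events that the protocol requires at the end-of-trial visit out of all adverse event and serious adverse event tables and out of the adverse event listings. This rests on the documents' own rules for recording and dating examination findings, and on reading *before* as it is written.

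The documents give no rate for such findings, so the count cannot be estimated. The effect per omitted subject, 0.5 or 1.0 percentage points for a preferred term, assumes the planned arm sizes and that the omitted report is that subject's only report of the term. The 5% example is an illustration, not a forecast. The correction should be made because safety counts ought to be complete and reproducible; no change in the trial's conclusions has been shown.

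**What to change.** In SAP 11.2, replace *before the end-of-trial visit* with *up to and including the end-of-trial visit (or the visit at which end-of-trial assessments are performed)*, in both the onset clause and the worsening clause. The words in brackets settle the cut-off for untriggered subjects. Add one line to SAP section 13 to record the departure from protocol 9.9.

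The cost is one phrase in two clauses and one line. No new data or outputs are needed, because adverse events are already collected until that visit. No protocol amendment is needed for the analysis, since SAP section 1 provides that the SAP carries the updated analyses where the two documents differ. Protocol 9.9 could be aligned if the protocol is amended for another reason.
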